4.2.3.10 Time to iCPD

The time to immune Clinical Progressive Disease (iCPD) is the length of time from start of treatment until the date iCPD assessed through iRECIST is obtained. Patients not obtaining iCPD will be censored on the date of their last tumor assessment.

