9.1.4 Immune RECIST (iRECIST)

RECIST 1.1 will be adapted to account for the unique tumor response characteristics seen with treatment of pembrolizumab. Immunotherapeutic agents such as pembrolizumab may produce antitumor effects by potentiating endogenous cancer-specific immune responses. The response patterns seen with such an approach may extend beyond the typical time course of responses seen with cytotoxic agents, and can manifest a clinical response after an initial increase in tumor burden or even the appearance of new lesions. Standard RECIST may not provide an accurate response assessment of immunotherapeutic agents such as pembrolizumab. Therefore, RECIST 1.1 will be used with the following adaptations:

- If radiologic imaging verifies initial progressive disease (PD), tumor assessment should be repeated ≥ 4 (iRECIST 4-8) weeks later in order to confirm PD with the option of continuing treatment per below while awaiting radiologic confirmation of progression.

At initial progressive disease based on RECIST 1.1 criteria, iRECIST: can have iUPD (Unconfirmed Progressive Disease). Imaging must then be repeated 4-8 weeks later. Progression is defined as the time of the first iUPD followed by the next confirmatory scan showing progression. Thus, iPFS is defined as the time to iUPD if the next scan (4-8 weeks later) confirms PD (state change from iUPD to iCPD, time to progression defined in this instance as iUPD). Note: following iUPD, if the next assessment is not a CPD, treatment can continue until iCPD is documented.

- iRECIST criteria:
 - For iUPD; if repeat imaging shows $< 20\%$ tumor burden increase compared to nadir, stable or improved previous new lesion (if identified as cause for initial PD), and stable/improved non-target disease (if identified as cause for initial PD), treatment may be continued/resumed.
 - NOTE; if repeat imaging confirms PD due to any of the scenarios listed below, patients will be discontinued from study therapy.

In determining whether or not the tumor burden has increased or decreased, site study team should consider all target lesions as well as non-target lesions.

Scenarios where PD is confirmed at repeat imaging (iCPD):

- Tumor burden remains $\geq 20\%$ and at least 5 mm absolute increase compared to nadir
- Non-target disease resulting in initial PD is worse (qualitative)
- New lesion resulting in initial PD is worse (qualitative)
- Additional new lesion(s) since last evaluation

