When feasible, patients should not be discontinued until progression is confirmed. This allowance to continue treatment despite initial radiologic progression takes into account the observation that some patients can have a transient tumor flare in the first few months after the start of immunotherapy, but with subsequent disease response. Patients that are deemed clinically unstable are not required to have repeat imaging for confirmation of progressive disease.

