- For a **clinically stable** subject with first radiologic evidence of progressive disease by RECIST 1.1 (i.e., **unconfirmed progression of disease or iUPD**), it is at the discretion of the site investigator to continue treating the subject with the assigned treatment per protocol until progression of disease (iCPD) is confirmed at least 28 days from the date of the scan first suggesting PD. If radiologic progression is confirmed by subsequent scan then the subject will be discontinued from trial treatment. If radiologic progression is not confirmed by iRECIST per the site, then the patient should resume or continue trial treatment and have their next tumor imaging according to the protocol schedule of every 9 weeks (end of every 3rd treatment cycle) until progression is confirmed at a later timepoint by the site. In applying iRECIST, the appropriate documentation at

each time point must be made (i.e. iSD, iUPR, iUCR). For a more comprehensive and detailed account of the application of RECIST 1.1 and iRECIST for in-study imaging assessments please refer to the imaging guide document Note that RECIST 1.1 must always serve as the primary imaging assessment guide up to the first indication of disease progression after which iRECIST may be used as described.

- Any subject deemed **clinically unstable** should be discontinued from trial treatment at 1st radiologic evidence of PD and is not required to have repeat imaging for PD confirmation.
- In subjects who discontinue study therapy without documented disease progression, every effort should be made to continue monitoring their disease status by tumor imaging using the same imaging schedule used while on treatment (every 9 weeks), until (1) the start of new anti-cancer treatment, (2) disease progression (3) death, or (4) the end of the study, whichever occurs first.

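### Time to iCPD is dated at the confirming scan, 4-8 weeks after the date the protocol gives to immune progression, and separately censors deaths and never re-scanned iUPD in an informative way

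*SAP*

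**What the plan says.** SAP 4.2.3.10 defines an interval that "is the length of time from start of treatment until the date iCPD assessed through iRECIST is obtained". Its only censoring rule is "Patients not obtaining iCPD will be censored on the date of their last tumor assessment". Death and new anticancer therapy are not mentioned.

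Protocol 9.1.4 dates immune progression differently: "Progression is defined as the time of the first iUPD followed by the next confirmatory scan showing progression". It adds that "iPFS is defined as the time to iUPD if the next scan (4-8 weeks later) confirms PD", with "time to progression defined in this instance as iUPD". On the gap between the two scans it says: "Imaging must then be repeated 4-8 weeks later".

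The protocol does not require a second scan for everyone. Section 9.1.4 states: "Patients that are deemed clinically unstable are not required to have repeat imaging for confirmation of progressive disease". Section 9.1.5 says that a clinically unstable patient "should be discontinued from trial treatment at 1st radiologic evidence of PD and is not required to have repeat imaging for PD confirmation".

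Two neighbouring SAP endpoints follow other rules. Duration of immune response (4.2.3.13) ends at death or at the iUPD that the next assessment confirms, whichever comes first, and has a new-therapy rule. Duration of iBOR (4.2.3.9) also ends at death and has a new-therapy rule.

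SAP 5.3 analyses Time to iCPD by Kaplan-Meier, with a median and 95% confidence interval. SAP 5.6.3 treats the exploratory endpoints descriptively. The protocol synopsis also lists PFS by iRECIST, but the SAP defines no such endpoint, so Time to iCPD is the SAP's only time-to-progression measure under iRECIST.

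**The concern.** There are two separate problems.

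The first is dating. For a patient whose progression is confirmed, the SAP starts counting progression at the second scan, while the protocol's general rule and SAP 4.2.3.13 use the first. One patient can then have immune progression on two dates within the same report.

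The second is censoring. Kaplan-Meier assumes that a patient censored at a given time has the same future risk as those still followed. A patient with iUPD who is too unwell to be re-scanned, or who dies before confirmation, does not. Censoring such patients takes the poorest outcomes out of the event count.

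Readers will naturally set Time to iCPD beside RECIST 1.1 PFS (SAP 4.2.3.2), which counts both PD and death. Part of any apparent gain under iRECIST would then come from the definition and not from the treatment.

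**Working it through.** The documents give no expected value for Time to iCPD, so there is no figure to reproduce.

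**Step 1: date shift.** SAP date minus protocol date = confirming scan minus iUPD scan = 4 to 8 weeks (protocol 9.1.4) when the next scan confirms. Table 13 of the protocol gives only a minimum of 4 weeks, and an iUPD-iUPD-iCPD sequence (SAP Table 3, Example 7) can take longer. For scale, using reference medians quoted in the protocol and 4.345 weeks per month:
- Ovarian reference cohort (1.5.2): 1.9 × 4.345 = 8.3 weeks, so the shift is 4/8.3 to 8/8.3, or 48% to 97% of the median.
- Mesothelioma reference cohort (1.5.4.3): 5.4 × 4.345 = 23.5 weeks, so the shift is 17% to 34%.

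**Step 2: what the censoring does at each scan.** Let p be the share of at-risk patients with first iUPD at a scan and u the share of those with no later scan. Ignore deaths, and assume that every re-scan confirms. The Kaplan-Meier factor for each scan is then:
- SAP rule: (1 − p)/(1 − pu), placed 4-8 weeks after the scan.
- Confirmed iUPD only, dated at iUPD, others censored there: 1 − p(1 − u).
- Confirmed or never re-scanned iUPD counted, dated at iUPD: 1 − p.

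With p = 0.5 (assumed), the estimated proportion without an event after two scans is:
- u = 20%: SAP (0.5/0.9)² = 0.31; confirmed only 0.6² = 0.36; all counted 0.5² = 0.25.
- u = 50%: SAP (0.5/0.75)² = 0.44; confirmed only 0.75² = 0.56; all counted 0.25.

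At u = 0 all three factors equal 0.5, and only the date shift is left. At u > 0 the SAP curve lies above the true 0.25. Confirmed-only dating steps down earlier but by less, because patients without a re-scan are still in the risk set when its events occur.

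**Step 3: illustration with deaths.** Kaplan-Meier simulation, 40,000 patients per scenario. Assumptions: exponential, independent progression and death; scans every 9 weeks ± 3 days; confirming scan uniform 4-8 weeks after iUPD; every re-scan confirms; unstable patients chosen at random; follow-up to 35 × 3 = 105 weeks. Fast scenario: PFS 1.9 and OS 13.1 months (ovarian reference). Slower scenario: 5.4 and 18 months (mesothelioma reference). Medians in weeks:

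| Scenario | u | SAP rule | Confirmed only, at iUPD | iUPD confirmed or never re-scanned, or death |
|---|---|---|---|---|
| Fast | 0% | 16.7 | 9.4 | 9.3 |
| Fast | 20% | 22.1 | 17.8 | 9.3 |
| Fast | 40% | 23.5 | 18.2 | 9.3 |
| Fast | 60% | 25.2 | 26.9 | 9.3 |
| Slower | 0% | 33.3 | 27.1 | 18.4 |
| Slower | 20% | 40.4 | 35.9 | 18.8 |
| Slower | 40% | 44.3 | 44.9 | 18.4 |
| Slower | 60% | 61.6 | 63.2 | 18.4 |

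The SAP median exceeds the last column by 7.4 to 15.9 weeks (fast) and 14.9 to 43.2 weeks (slower). If never re-scanned iUPD is counted but deaths stay censored, the slower median is about 27, so counting death accounts for roughly 27.0 − 18.4 = 8.6 weeks there. Medians jump between scan times on a 9-week grid; the direction is steadier than the sizes. Re-dating alone does not shorten the median at u = 60% in either scenario, nor at 40% in the slower one.

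**The case against.** The best defence is the name. A time to iCPD that ends when iCPD is obtained is literal, and the protocol lists the endpoint without defining it; the rule in 9.1.4 is for progression and iPFS. Leaving out deaths is the ordinary difference between time to progression and PFS, and deaths are counted in RECIST PFS (SAP 4.2.3.2) and OS (SAP 4.2.3.6). The endpoint is one of several exploratory summaries in single-arm cohorts, with no test.

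Much of this stands and limits the point, but it leaves the mismatch with SAP 4.2.3.13 unexplained. It also does not cover iUPD that was never re-scanned, which is an observed worsening and not a competing event.

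Three stronger readings are tempting, and the documents do not support them:
- A reader might infer that the censoring breaches the protocol. It does not. Protocol 9.1.4 counts iUPD only if the next scan confirms it, and it has no rule on death for iRECIST progression. The conflict is about dating only.
- A reader might infer that unstable patients can never reach iCPD. Protocol Table 13 allows a repeat scan at the physician's discretion.
- A reader might take one simulated gap as the cost of departing from the protocol. Large gaps arise only when unconfirmed iUPD, death or both count as events, which is not the protocol's rule. Against confirmed-only dating, the difference shrinks and can reverse as u rises.

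**Conclusion.** The point holds as two findings of different standing. The dating conflict follows from the text: 4-8 weeks late for each event confirmed at the next scan, against both protocol 9.1.4 and SAP 4.2.3.13. The censoring is a source of bias and an inconsistency with SAP 4.2.3.9 and 4.2.3.13. It also sits badly with SAP 5.2.2, which treats a patient who dies or stops for an AE before any assessment as having progressed in the absence of other data.

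Relative to counting never re-scanned iUPD and death, the SAP rule gave longer times in every scenario tried. The amount rests on assumed progression and death rates and on an assumed unconfirmed share of 0-60%, none of which the documents give for this trial. The consequence is limited to an exploratory Kaplan-Meier estimate. RECIST 1.1 PFS, OS, the primary ORR test and the Simon decisions are untouched. The change is worth making but not critical.

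**What to change.** Amend SAP 4.2.3.10 as follows:
- Date the event at the iUPD that is subsequently confirmed, and state which date applies to an iUPD-iUPD-iCPD sequence.
- Count death as an event, as in 4.2.3.13.
- Count an iUPD with no later scan as an event at that iUPD. Describe this as a bias correction, not as the protocol's rule.
- Keep patients alive whose iUPD was re-scanned and not confirmed censored at their last scan.
- Censor patients who start new therapy without an earlier event at the last scan before it.
- Correct the expansion of iCPD: 4.2.3.10 reads Clinical, the abbreviation list Confirmed.

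If literal time to confirmation is intended, label it as such and add the protocol's iPFS with the rules above.

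The cost is SAP wording and programming; the scan, death and new-therapy dates are already collected. Reported times become shorter, and with death counted the measure is in effect an iPFS, which its label should make clear.

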4.2.3.11 Immune Clinical Benefit Rate (iCBR)

The iCBR is defined as the percentage of patients with the best measurement of response categorized as iCR, iPR or iSD. Note that iSD requires no confirmation as is required for the immune best overall response of either iCR or iPR. The first tumor assessment is planned to occur 9 weeks after first dose and therefore, iSD documented at the first assessment would typically qualify as iSD. However, an iSD with actual assessment time less than 6 weeks after first dose will not be qualified as iSD. Patients with no post-baseline tumor assessments are considered to have achieved no clinical benefit according to iRECIST.

4.2.3.12 Time to immune response

The time to immune response is defined as the length of time from start of treatment until the date of the first documented iCR or iPR assessed through iRECIST. iCR or iPR requires confirmation on imaging dates that are at least 4 weeks apart. Once it is confirmed, the first documented iCR or iPR will be considered the start of the response.

Patients not obtaining an overall response (iCR or iPR) will be censored at the the date of their last tumor assessment.

4.2.3.13 Duration of immune response

Duration of immune response is defined as the length of time from the first date of confirmed iCR/iPR to the date of death or the date of first documented tumor progression (iUPD) provided that iCPD is confirmed at the next assessment, whichever is earlier, using iRECIST. Patients who remain alive and do not progress are censored on the date of their last tumor assessment. Patients who start a new therapy without a prior iUPD are censored at the last tumor assessment prior to initiating the subsequent anticancer therapy. Response duration is only evaluated in patients with an overall immune response of iCR or iPR.

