6.3 Procedures After Active Protocol Treatment Phase

Patients will be treated until unacceptable toxicity, confirmed disease progression (refer to [Section 9.1.5](#)), or another criterion for treatment discontinuation is encountered.

Patients who discontinue treatment because of adverse events will be followed until resolution to baseline or stabilization of the adverse event. All patients will return for a safety evaluation 30 days (+ 7 days) following the last dose of study drug.

Those patients that are discontinued from study treatment due to reasons other than disease progression, but have not withdrawn consent to be followed for survival will need to be followed every 30 days until documentation of disease progression or initiation of a new therapy for their disease. Once there is documentation of disease progression or initiation of a new therapy for their disease, the patient will move into the long-term survival follow up phase of the study.

All patients will be followed every 3 months for survival.

Patients will be considered lost-to-follow-up only if no contact has been established by the time the study is completed such that there is insufficient information to determine the patient's status at the end of the study. Investigators should document attempts to re-establish contact with missing patients throughout the study period. If contact with a missing patient is re-established, follow-up should resume according to the protocol.

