9.1.3 On-Study Tumor Imaging

Following the screening CT scans, patients are to have repeat radiological assessments at the end of Cycle 3 [9 weeks (63 days \pm 3 days) from Cycle 1 Day 1]. Subsequent radiological assessments are to be performed every 9 weeks (at the end of every 3rd treatment cycle) until documentation of disease progression. If cycles become delayed, for whatever reason, the imaging schedule will as a default follow a nine-week pattern regardless of where in terms of cycles the subject is. If there is a large mismatch the PI can discuss frequency with the medical monitor

Per RECIST 1.1, if a patient has a documented partial or complete response, a

confirmatory tumor radiological assessment is to be performed not less than 4 weeks from the date the response was first documented.

Patients are to continue to have tumor assessments performed until whichever of the following occurs first:

- Site-assessed disease progression is documented
- The start of new anti-cancer treatment
- Withdrawal of consent
- Death
- The end of the study

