4.2.3.9 Duration of iBOR

The duration of iBOR is defined as the length of time from the date when iBOR is first documented until the date of death or the date when a change in disease state using iRECIST is objectively documented, whichever is earlier. Patients who remain alive and do not change from iBOR in disease state are censored on the date of their last tumor assessment. Patients who start a new therapy and do not change from iBOR in disease state are censored at the last tumor assessment prior to initiating the subsequent anticancer therapy. Duration of iBOR is only evaluated in patients with a documented disease state.

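### SAP 4.2.3.13: a responder whose iUPD is never re-scanned has no progression event, so duration of immune response can run on to death through later therapy (minor, exploratory endpoint)

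*SAP*

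**What the plan says.** SAP 4.2.3.13 measures duration of immune response from the first date of a confirmed iCR or iPR. It recognises two ending events: death, or "the date of first documented tumor progression (iUPD) provided that iCPD is confirmed at the next assessment, whichever is earlier, using iRECIST". Two censoring sentences follow. The general one is "Patients who remain alive and do not progress are censored on the date of their last tumor assessment". The one for later treatment is "Patients who start a new therapy without a prior iUPD are censored at the last tumor assessment prior to initiating the subsequent anticancer therapy".

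The protocol sets when a second scan is taken. Section 9.1.4 states: "Patients that are deemed clinically unstable are not required to have repeat imaging for confirmation of progressive disease". Section 9.1.5 says that such a patient "should be discontinued from trial treatment at 1st radiologic evidence of PD and is not required to have repeat imaging for PD confirmation". Table 13 leaves repeat imaging of unstable patients to the physician. Section 9.1.3 lists "The start of new anti-cancer treatment" among the points at which tumor assessments end. Deaths are still collected, because section 6.3 says "All patients will be followed every 3 months for survival".

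Two neighbouring endpoints are written differently. Duration of iBOR (SAP 4.2.3.9) has a new-therapy rule with no restriction on earlier iUPD; it opens "Patients who start a new therapy and do not change from iBOR in disease state are censored at the last tumor assessment prior to initiating". Duration of response by RECIST 1.1 (SAP 4.2.3.5) takes the first PD as the event and needs no confirmation.

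**The concern.** The SAP makes progression depend on a confirming scan, and the protocol says that some patients need not have that scan. For those patients the iUPD does not count as progression, yet it is enough to remove them from new-therapy censoring. Whatever happens between the iUPD and death is then credited to the immune response, even on a different drug.

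What is at stake is how the iRECIST results are read beside the RECIST results. Immune duration of response could be longer simply because a scan was not taken, and a reader could take the difference as evidence of immune benefit.

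**Working it through.** SAP 4.2.3.13 states no figure, so there is nothing to reproduce. The check applies the rules to one patient and then illustrates the size.

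**Step 1. One patient under each rule.** Take first iPR at week 9, confirmed at week 13; centrally read iUPD at week 36 with clinical deterioration and no re-scan; new therapy at week 39; death at week 80.

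- Progression event: none, because no next assessment confirms iCPD.
- New-therapy censoring: does not apply, because there is an earlier iUPD.
- General censoring: does not apply, because the patient has died.
- Remaining event: death. Duration = 80 − 9 = 71 weeks.
- Duration to the iUPD = 36 − 9 = 27 weeks. RECIST duration (SAP 4.2.3.5) is also 27 weeks, since the first PD is the event.

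The excess is 80 − 36 = 44 weeks. Counting from the confirming scan at week 13 changes both durations (67 and 23 weeks) but not the excess. The same patient alive at cut-off is censored at week 36, the scan that showed progression, and contributes no event.

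**Step 2. Does another rule close the gap?**

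- SAP 5.2.2 treats some patients as progressed, but only for death or an adverse event ending treatment before any post-baseline assessment. A confirmed responder is past that point.
- Protocol 9.1.4 dates iPFS at the iUPD if the next scan confirms it, and is silent when there is no next scan.
- SAP 5.4.1 rules out imputing missing values in the efficacy analysis.
- SAP Table 3, Example 8 anticipates an iUPD followed only by non-evaluable time points, but assigns only iBOR there.

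The restriction also catches a patient with an early iUPD, then a confirmed iPR, then new therapy without a second progression. That patient is not censored at new therapy either.

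**Step 3. Size across a cohort: deaths observed.** Inputs:

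- True median time from response to iUPD: 5.4 months, the pembrolizumab cervical figure in protocol 1.5.3. In weeks, 5.4 × 30.4375 / 7 = 23.5.
- Share u of responders with an un-rescanned iUPD: assumed, 10 to 40%.
- Median survival m after that iUPD: assumed, 4 to 39 weeks.
- Times are assumed exponential and all such patients are followed to death.

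With a = ln 2 / 23.5 and b = ln 2 / m, the analysed median solves

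(1 − u)·exp(−at) + u·[b·exp(−at) − a·exp(−bt)] / (b − a) = 0.5.

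| m (weeks) | u = 10% | u = 20% | u = 40% |
|---|---|---|---|
| 4 | 24.2 | 24.8 | 26.1 |
| 8 | 24.8 | 26.1 | 28.7 |
| 13 | 25.4 | 27.3 | 31.4 |
| 26 | 26.1 | 29.1 | 36.0 |
| 39 | 26.5 | 30.0 | 39.1 |

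**Step 4. Size across a cohort: patients alive.** If a share u is instead censored at the iUPD, the event rate in the same model falls by the factor (1 − u). The Kaplan-Meier median is then 23.5 / (1 − u): 26.1, 29.4 and 39.2 weeks for 10, 20 and 40%. This branch also pushes upward, although no time after the iUPD is counted.

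**Step 5. How many responders.** At the target rates in SAP Table 4, expected RECIST responders are 27 × 0.20 = 5.4, 26 × 0.25 = 6.5 and 25 × 0.30 = 7.5 per cohort. One or two such patients can move a median based on so few.

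**The case against.** The strongest objection is that the authors may have meant something else. Limiting new-therapy censoring to patients with no earlier iUPD makes sense if they regarded a patient with an iUPD as already progressed on that date. The worked patient would then have 27 weeks. This is a plausible account of the intent, but it conflicts with the explicit condition that the next assessment confirm iCPD. A programmer following the text would not count the event.

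Several other points stand and limit the claim.

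- Repeat imaging of unstable patients is optional, not barred. Protocol 9.1.4 prefers confirmation before discontinuation where feasible. A reader might infer that such an iUPD can never become iCPD; the documents say only that it need not be confirmed.
- Stopping and re-scanning follow the site read, whereas SAP 4.2.3 analyses the independent radiologist's read. A site PD that is not a central iUPD leaves new-therapy censoring in force. The imaging charter may say more and is not available here.
- A reader might infer that the fastest clinical progressors receive the longest durations. That does not follow: they receive time to iUPD plus remaining survival, which may be short in unstable patients. With 4 to 8 weeks of median survival and a 10 to 20% share, the median is only 24.2 to 26.1 weeks.
- Sampling noise is larger than the shift. With six responders and the same model, the sample median ranges from about 7 to 59 weeks (95%) with no bias at all.
- The endpoint is exploratory and descriptive (SAP 4.2.2.3 and 5.6.3). RECIST duration of response, a secondary endpoint, does not have this gap.
- Counting an unconfirmed iUPD as an event is a convention, and others could be defended.

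**Conclusion.** The rule is wrong as written, and the matter is minor. Under SAP 4.2.3.13 a responder whose centrally read iUPD is not re-scanned has no progression event and is outside new-therapy censoring. Death then ends the response, however late and on whatever therapy; a survivor is censored at the last scan, normally the one that showed progression. Both routes can bias the duration upward, so it may exceed RECIST duration for reasons unrelated to immune benefit. The documents do not support saying that it will.

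For the single patient the error is 71 weeks against 27. For a cohort, a true median of 23.5 weeks becomes about 24 to 39 weeks. That range rests on exponential times and on assumed shares and post-iUPD survival, none of which the documents supply. The primary ORR analysis and the Simon decision rules do not use this endpoint.

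**What to change.** Make two changes in SAP 4.2.3.13, before database lock.

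1. Count as an event, dated at the iUPD, any iUPD after response that is not followed by a later iCR, iPR or iSD assessment when the patient stops for progression, starts new therapy or dies.
2. Delete the qualifier that limits new-therapy censoring to patients with no earlier iUPD. A patient who starts new therapy without a counted progression is then censored at the last tumor assessment before it, in line with SAP 4.2.3.9.

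The worked patient then has 27 weeks, whatever the date of death. The cost is two sentences and a small programming change; no visit, scan or treatment rule is touched. The downside is that the reported duration of immune response may become shorter.
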